8.2. Primary Endpoint

The primary efficacy endpoint is the percentage of patients achieving an absolute SALT score of ≤ 20 at Week 24 (i.e., the binary endpoint denoting a SALT score ≤ 20).

8.2.1. Computation of the Primary Endpoint

The SALT is a measure of hair loss that quantifies the amount of scalp surface without hair in a pre-specified quadrant of the scalp (right side, top, left side, back), that is further summed after applying a quadrant-specific multiplier indicative of scalp surface area contribution, to provide an overall score of total hair loss. A total SALT score equal to 0% indicates complete hair growth. A total SALT score equal to 100% indicates complete hair loss. An example of the SALT assessment can be found in Appendix 17.2 of protocol. The overall total SALT score is calculated in the eCOA system and will not re-derived. SALT scores are considered missing if the overall total could not be calculated.

The primary endpoint is derived by categorizing the individual overall SALT scores at Week 24 (≤ 20 versus > 20).

A multiple imputation (MI) approach will be used to estimate missing SALT scores.

One hundred independent imputations will be done with SAS® PROC MI using the Fully Conditional Specification (FCS) regression method. The FCS method combines both the monotone and arbitrary missing data patterns into one procedure, imputing missing values with a sequential regression approach.

For the primary efficacy analysis, missing SALT scores will be imputed under a missing at random (MAR) assumption. This assumes that patients who have missing data would have similar SALT scores as other patients in their respective treatment arm who have complete data. Any missing post-baseline SALT scores will be imputed to better inform the estimates of Week 24 missing SALT scores. Patients who have discontinued treatment but remain on study will not have their SALT scores censored, but any arbitrary missing SALT scores after the patient discontinued treatment will be imputed in the same manner. Utilizing the FCS method, missing SALT scores will be imputed in a sequential manner using regression models with baseline SALT score and the observed or imputed values of previous visits as covariates. Imputations will be implemented separately for each treatment under the assumption that different treatments may have distinct posterior distributions.

In addition, prior to database lock, the classification of the missing data pattern for missing SALT scores will be finalized based on blinded data review and documented as either considered to be missing at random (MAR) or potentially missing not at random (MNAR), consistent with general categories of reasons for missingness. Subjects with missing data due to COVID-19 will have data reviewed to determine the specific limitation imposed by COVID-19 leading to the inability to have captured the protocol-specified assessments. For example, missing at random will be considered plausible for COVID-19 related reasons such as site closures and travel limitations. In general, however, if a MAR assumption is not considered plausible, MNAR will be assumed. Patterns of missing values across visits will be listed and summarized with numbers and percentages by treatment and visit.

Multiple imputation will be done using the Efficacy Population and will not be repeated separately for the Per Protocol Population.

8.2.2. Primary Analysis of the Primary Endpoint

Pairwise treatment group differences from placebo will be assessed with the Mantel-Haenszel test (common risk difference) using baseline scalp hair loss (partial vs complete/near-complete) as the stratification factor, for each active treatment group versus placebo.

For each imputed dataset, treatment differences will be assessed using the Mantel-Haenszel estimate of a common risk difference, with the variance estimator (used to construct confidence limits for the Mantel-Haenszel estimate of the common risk difference in the SAS FREQ Procedure). The resulting 100 estimates of the treatment differences and standard errors will then be combined using SAS PROC MIANALYZE. The following SAS options for PROC FREQ will be used to estimate a common risk difference, confidence intervals, and p-values by imputation for placebo compared to each dose separately:

```
proc freq data = <> ;  
  by IMPUTATION;  
  tables STRATA*TREATMENT*RESPONSE / commonriskdiff(cl=mh test=mh);  
  run;
```

The observed number and percentage of patients with an absolute SALT score ≤ 20 among non-imputed data will be reported by treatment group along with the appropriate p-value, the combined treatment differences, combined standard errors, and 95% confidence intervals (CI).

This analysis will be completed for the Efficacy Population and the Per Protocol Population. The analysis utilizing the Per Protocol Population is considered supportive. The results may also be displayed graphically.

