12. STATISTICAL METHODS

12.1. Sample Size Rationale

Power is calculated for the Primary Efficacy Endpoint for the chi-square test using a 2-sided significance level of 0.025. Based on Phase 2 results, the percentage of patients achieving an absolute SALT score ≤ 20 at Week 24 is assumed to be 40%, 25%, and 10% for the CTP-543 12 mg, CTP-543 8 mg BID, and placebo groups, respectively. Patients will be randomized in a 3:5:2 ratio with a total N of approximately 700 patients (i.e., 210 for 12 mg BID, 350 for 8 mg BID, and 140 for placebo BID). These sample sizes will provide >99% power for the comparison of CTP-543 12 mg BID versus placebo and approximately 94% power for the comparison of CTP-543 8 mg BID versus placebo.

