6.2. Demographic and Other Baseline Characteristics

Demographic characteristics (ie, sex, ethnic origin, race, date of birth, and calculated body mass index) will be collected at the Screening Visit, between Day -28 and -1, and detailed on the eCRF. Demographic characteristics will be summarized using descriptive statistics for all randomized patients by treatment group and overall.

Baseline characteristics will be summarized using descriptive statistics for all randomized patients by treatment group and overall and will include the following:

- baseline total SALT score
- Alopecia areata classification (randomization strata via IWRS): partial scalp hair loss (SALT \geq 50 and $<$ 95); complete or near-complete scalp hair loss (SALT \geq 95)
- duration of current episode in years (calculated as: [date of randomization – date of current episode onset + 1] / 365.25)
- current nail involvement: yes; no (collected via eCOA system as ‘HAND IMAGE CAPTURE’)
- nasal hair involvement: yes; no (collected on the Physical Examinations eCRF page)
- eyebrow involvement: yes; no (collected as part of the BETA assessment)
- eyelash involvement: yes; no (collected as part of the BELA assessment)
- whether the patient has experienced any past and/or concomitant diseases, conditions, or exposures to serious infections such as HIV, or past surgeries: yes; no (collected via the Medical History Summary eCRF page)

Other co-morbidities may be identified and included as baseline characteristics.

All demographics and baseline characteristics will also be listed within a by-patient data listing for all randomized patients.

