8.3. Key Secondary Endpoints

See Section 8.1.4 and Figure 1 below for hierarchical testing.

Figure 1: Hierarchical Testing

8.3.1. Hair Satisfaction Patient Reported Outcome (SPRO) at Week 24

The first key secondary endpoint is the percentage of responders per the SPRO at Week 24. The SPRO is a single item questionnaire answered by the patient, designed to measure how satisfied alopecia areata patients are with their hair at the time of the assessment. The SPRO responses are on a scale of 1-5, where 1 = very satisfied, 2 = satisfied, 3 = neither satisfied nor dissatisfied, 4 = dissatisfied, and 5 = very dissatisfied. An example of the SPRO assessment can be found in Appendix 17.4.1 of the protocol.

A responder is defined as patients with answers of “very satisfied” or “satisfied” at Week 24 on the SPRO. This endpoint will be assessed similar to the primary analysis for the primary endpoint, according to Section [8.2.2](#).

Missing data will be imputed similarly to the primary endpoint according to Section [8.2.1](#). However, since the SPRO scale is ordinal, the FCS logistic regression method will be used in lieu of the FCS regression method. The missing SPRO scores will be imputed in a sequential manner using logistic regression models with baseline SALT score, baseline SPRO score, and the observed or imputed SPRO values of previous visits as covariates.

The observed number and percentage of SPRO responders by treatment group will be reported along with the appropriate p-values. Both CTP-543 doses will be tested in parallel against placebo with a ≤ 0.025 alpha level. This analysis will be completed for the Efficacy Population and the Per Protocol Population. The Per Protocol Population will be considered supportive. If the primary endpoint is unsuccessful, nominal p-values will be reported.

8.3.2. SALT Score ≤ 20 at Weeks 20, 16, 12, and 8

The next key secondary endpoints are the percentage of patients achieving an absolute SALT score of ≤ 20 (i.e., the binary endpoint denoting a SALT score ≤ 20) at Weeks 20, 16, 12, and 8. Missing data will be imputed according to Section [8.2.1](#). These endpoints will be assessed according to Section [8.2.2](#). If the primary endpoint and first key secondary endpoint are unsuccessful, nominal p-values for the SALT key secondary endpoints will be reported. This analysis will be completed for the Efficacy Population and the Per Protocol Population. The Per Protocol Population will be considered supportive.

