8.4.2. Secondary SPRO Endpoints

The following secondary SPRO responder endpoints will be assessed:

- Percentage of responders at Weeks 12, 16, and 20, where responders is defined as “very satisfied” or “satisfied”
- Percentage of patients achieving a ≥ 2 -point change from baseline in the SPRO scale at Weeks 12, 16, 20, and 24

In addition, the continuous secondary SPRO endpoint of change from baseline at Weeks 12, 16, 20, and 24 will be assessed with a MMRM. The model will include fixed factors for treatment group, study visit, and treatment by study visit interaction, with baseline SALT score and baseline SPRO score as covariates. Imputed values will not be used for the MMRM.

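### The confirmatory responder tests adjust only for the two-level hair-loss stratum; adding continuous baseline SALT, and baseline SPRO for the SPRO endpoint, could gain some precision at low cost

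*SAP*

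**What the plan says.** The primary analysis in SAP 8.2.2 is a Mantel-Haenszel common risk difference "using baseline scalp hair loss (partial vs complete/near-complete) as the stratification factor, for each active treatment group versus placebo". The SAS code there crosses stratum, treatment and response and has no other baseline term. For SPRO at Week 24, SAP 8.3.1 states "This endpoint will be assessed similar to the primary analysis for the primary endpoint", and SAP 8.3.2 refers SALT of 20 or less at Weeks 20, 16, 12 and 8 to the same section. All six alpha-controlled tests per dose therefore share this adjustment. SAP 8.2.4 lists no secondary analysis of the primary endpoint.

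Elsewhere the SAP uses more baseline information. Continuous baseline SALT is in the SALT imputation model (8.2.1), and baseline SALT and baseline SPRO are in the SPRO imputation model (8.3.1). The mixed model for change in SPRO is fitted "with baseline SALT score and baseline SPRO score as covariates" (8.4.2), and the other continuous secondary models also include baseline SALT. SAP 6.2 derives "duration of current episode in years", which enters no model.

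**The concern.** SALT of 20 or less is an absolute target, so how far a patient must improve depends on the starting score. The partial stratum runs from 50 to just under 95 and treats all those patients alike. If baseline SALT predicts response within that stratum, a test that uses it would give a narrower interval for the same marginal risk difference. For SPRO, the responder definition sets no condition on the baseline answer, which makes baseline SPRO a natural covariate.

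The stakes lie mainly with 8 mg, which has the smaller assumed effect. Under SAP 8.1.4 a single p-value above 0.025 ends alpha protection for that dose's later endpoints, so a few points of power could decide a step.

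**Working it through.** **Inputs from Protocol 12.1.** "Power is calculated for the Primary Efficacy Endpoint for the chi-square test using a 2-sided significance level of 0.025". Response "is assumed to be 40%, 25%, and 10% for the CTP-543 12 mg, CTP-543 8 mg BID, and placebo groups, respectively". Arms: "210 for 12 mg BID, 350 for 8 mg BID, and 140 for placebo BID".

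**1. The plan's own power, 8 mg v placebo.**
- Pooled rate = (14 + 87.5)/490 = 0.2071.
- Null SE = √(0.2071 × 0.7929 × (1/140 + 1/350)) = 0.0405.
- Alternative SE = √(0.09/140 + 0.1875/350) = 0.0343.
- z = 2.2414 for two-sided 0.025.
- Pooled power = Φ[(0.15 − 2.2414 × 0.0405)/0.0343] = 95.8%.
- With a continuity correction of 0.005 it is 94.3%, which matches the stated figure of about 94%.
- Unpooled power = Φ(0.15/0.0343 − 2.2414) = 98.3%. This form is closer to the Mantel-Haenszel test actually planned.
- For 12 mg, every variant exceeds 99%.

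**2. How coarse the stratum is.** The required relative reduction is 1 − 20/baseline:
- SALT 50: 60%
- SALT 94: 78.7%
- SALT 95: 78.9%
- SALT 100: 80%

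Nearly all of the spread in required improvement lies inside the partial stratum.

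**3. What adjustment could gain.** Simulations used 350 v 140 patients and 2,000 to 6,000 trials per scenario. They compared the two-stratum Mantel-Haenszel risk difference with a risk difference standardised from a logistic model. That model held stratum, baseline SALT and episode duration, with baseline SPRO added in some runs.

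The following are assumptions, because the documents give none of them: 35% to 60% of patients at SALT 95 or more, the covariate distributions (for example, SALT uniform from 50 to 95 in the partial stratum and duration log-uniform from 0.5 to 10 years), and the effect sizes (in one set, log-odds of −0.25, −0.45 and −0.6 per 10 SALT points for weak, moderate and strong).

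Relative efficiency (RE) is the Mantel-Haenszel variance divided by the adjusted variance. Extra patients = 490 × (RE − 1). Ranges cover several sets of runs; for example, variance ratios of 0.967 and 0.864 give RE of 1.03 and 1.16.

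| Assumed effect beyond the stratum | RE | Extra patients | Power change, 25% v 10% | Power, 20% v 10% (assumed) |
|---|---|---|---|---|
| None | 0.99–1.00 | none | about 0 | about 0 |
| Weak | 1.00–1.02 | 0–10 | +0.1 to +0.2 | 79.5→79.1; 78.0→77.6 |
| Moderate | 1.03–1.06 | 15–29 | +0.4 to +0.5 | 82.4→83.8; 78.2→80.2 |
| Strong | 1.08–1.16 | 39–78 | +1.0 to +1.1 | 79.4→83.4; 82.0→87.4 |

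**4. Closed-form check.** Power = Φ[(difference/SE) × √RE − 2.2414], unpooled.
- At 25% v 10%: 98.3% at RE 1.00, 98.7% at 1.05, 99.3% at 1.15.
- At 20% v 10% (SE 0.0332): 78.0%, 80.2% and 83.9%.
- The 95% half-width for 8 mg at planned rates is 1.96 × 0.0343/√RE: 6.7, 6.6 and 6.3 points.

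**5. Type I error.** At nominal 2.5%, four sets of null runs gave, for Mantel-Haenszel v adjusted, 3.1 v 2.9, 2.75 v 2.68, 2.6 v 3.0 and 3.2 v 3.3 (per cent). The methods differ by at most 0.4 points, in either direction. With 6,000 trials, simulation error is about √(0.025 × 0.975/6,000) = 0.2 points per rate.

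**6. Sparse visits.** In the strong case (40% at SALT 95 or more), the covariates explained 15.6% of outcome variance within strata on 8 mg (25% response) but 11% on placebo (10% response). Explained variance is lower where responders are fewer. If placebo response at Week 8 were 1% or 2% (assumption), the chance of no responder among 140 would be 0.99^140 = 24% or 0.98^140 = 6%. A logistic model may then not be estimable.

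**The case against.** The strongest reply is that nothing is broken. The planned test uses the randomisation factor, needs no outcome model, gives a risk difference directly and agrees between protocol and SAP. Planned power is already about 94% for 8 mg and above 99% for 12 mg. No document shows that baseline SALT within a stratum, episode duration or baseline SPRO predicts response, and with no or weak effects the gain is nil. All of that stands and limits the point to efficiency.

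A reader might infer that the plan ignores baseline SALT and loses precision for nothing. The documents do not support that. The stratum is itself baseline SALT cut at 95, and the continuous score informs imputed values, although only for missing data. Nor is simplicity worth nothing.

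A reader might also infer that the SPRO responder definition is faulty because a patient already satisfied at Baseline would count as a responder. The documents do not say how many such patients there are, and all patients enter with SALT of 50 or more. SAP 8.4.2 covers change through a responder endpoint of at least 2 points and a baseline-adjusted mixed model. What remains is only that baseline SPRO is available as a covariate.

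Two practical objections also stand. A fallback without a fixed trigger would add a data-dependent choice of estimator inside the testing hierarchy. And the early visits, where power is likely lowest, are where the fallback would most often apply.

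**Conclusion.** The concern holds as a modest efficiency improvement. The planned test has no bias, and the null runs show no type I error problem specific to it. Whether adjustment helps depends on prognostic strength that the documents do not give.

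Under the assumed scenarios, relative efficiency is about 1.00 to 1.02 with no or weak effects, 1.03 to 1.06 with moderate and 1.08 to 1.16 with strong effects. At the planned 25% v 10% that is worth at most about 1 power point. At an assumed 20% v 10% it is about 0 to 5 points in simulation, and up to about 6 by formula. The 12 mg decision at Week 24 is unaffected. Little should be expected at sparse early visits, and the gain for the SPRO endpoint has not been quantified.

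**What to change.** Before unblinding, amend SAP 8.2.2, 8.3.1 and 8.3.2 as follows:

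- Estimate each risk difference by standardising a logistic model over the trial population. Include treatment, randomisation stratum and continuous baseline SALT, plus baseline SPRO for the SPRO endpoint. Log episode duration is optional, since nothing in the documents shows that it is prognostic. If it is used, add it to the imputation models too.
- Use an influence-function standard error with a stated small-sample correction, and combine over the 100 imputations with PROC MIANALYZE. The target stays the marginal risk difference.
- Keep the two-stratum Mantel-Haenszel result as supportive.
- Set the fallback to Mantel-Haenszel by a fixed number of observed responders, counted blinded and pooled over arms. Apply it to all imputations of a visit together, so that the estimator cannot differ between imputations.

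If the sponsor prefers to keep the planned test as primary, the adjusted estimate could be prespecified as supportive in SAP 8.2.4. That helps interpretation but does not change the power of the confirmatory tests.

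The cost is SAP text, programming and validation, with no new data or patients. The price is reliance on an outcome model and one more rule to prespecify.

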For tests of hypothesis of treatment group differences, the associated p-value will be reported in rounded format. All p-values will be rounded to four decimal places after assignment of statistical significance; p-values that round to 0.0000 or are reported by SAS as zero will be presented as “≤0.0001”; p-values that round to 1 or are reported by SAS as 1 will be presented as “>0.9999”. P-values which are significant at a 0.05, 0.025, 0.01, 0.001, or 0.0001 level will be marked with asterisks. P-values which cannot be determined will be displayed as “NA”. P-values are descriptive for outcomes and analyses not included in the multiplicity algorithm.

Date of last dose is collected on the *Treatment Discontinuation/Completion* eCRF page. For patients with missing or partial date of last dose, the date of last dose (ie, treatment end date) will be imputed. Date of last dose will be imputed as follows:

Concert Pharmaceuticals, Inc.
Statistical Analysis Plan – CP543.3001

- Derive the number of tablets taken at the last visit as the dispensed amount minus the returned amount. For treatment compliance (Section 7.3) and exposure (Section 9.2), if the returned amount is missing, it will be assumed that zero tablets were taken. Otherwise, it will be assumed that 60 tablets were taken.
- An estimated date of possible last dose will be calculated by adding the number of tablets taken divided by 2 to the visit date associated with the last visit where drug accountability was collected.
- If there is a partial date of last dose, missing day will be imputed using the day from treatment start date, or the last day of the month if that month has fewer days than the treatment start month.
- Treatment end date will be the minimum of the partial date of last dose, calculated estimated date of possible last dose, and collected study discontinuation/completion date.

Summary tables and data listings:

- Unless otherwise specified, no preliminary rounding will be performed; rounding will only occur after analysis.
- Data from patients excluded from an analysis population will be presented in the data listings but will not be included in the calculation of summary statistics, where applicable.

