8.1.4. Multiple Comparisons/Multiplicity

Hierarchical testing will be used to control for multiple comparisons (Figure 1). For the primary efficacy analysis and the key secondary efficacy analyses, a ≤ 0.025 (two-sided) alpha-level will be allocated to each dose for comparison with placebo to adjust for multiplicity of testing associated with two doses. Once $p>0.025$ is observed for a treatment group comparison, inference for additional endpoints is no longer alpha-level protected for that dose group; however, nominal p-values will still be reported.

Subsequently, conditional upon significance (≤ 0.025) for the primary endpoint and first key secondary endpoint for each dose, a linear hierarchical testing approach with ≤ 0.025 (two-sided) alpha-level will be used to test the remaining key secondary endpoint comparisons versus placebo. Once $p>0.025$ is observed for a treatment group comparison, inference for additional endpoints is no longer alpha-level protected for that dose group; however, nominal p-values will still be reported.

All other statistical tests outside of the hierarchy will be carried out at a two-sided significance level of ≤ 0.05 . Nominal p-values will be presented without adjustment for multiple comparisons.

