8.2.3. Sensitivity Analyses of the Primary Analysis

Sensitivity analyses of the primary efficacy endpoint will be conducted to evaluate the robustness of study results under different assumptions and imputation algorithms. For the primary endpoint, categorized as absolute SALT score ≤ 20 at Week 24, the following sensitivity analyses will be performed for the Efficacy Population only.

Sensitivity 1: Multiple imputation; missing not at random (MNAR)

This sensitivity analysis is an implementation of a pattern mixture model that draws from different populations based on the reason for withdrawal from study. Patients who discontinued the study early due to a treatment-emergent adverse event (including COVID-19) or due to lack of efficacy will be considered MNAR. Treatment-emergent adverse event and lack of efficacy are reasons collected under “If 'Withdrew Consent', specify reason” on the *Study Discontinuation/Completion eCRF* page.

For patients who discontinued the study early due to a treatment-emergent adverse event or lack of efficacy, SALT scores missing after discontinuation will be imputed using the control arm. This assumes that patients, regardless of treatment, who discontinue the study early for those reasons would have similar SALT scores to placebo patients with complete data.

For patients who discontinued the study due to reasons other than treatment-emergent adverse event or lack of efficacy, missing SALT scores after subjects discontinue the study early will be multiply imputed from subjects within the same treatment group who have complete data at that time. Terms will include baseline values and the weekly data through the time point being imputed.

The proportion of patients who have a SALT score ≤ 20 will be calculated for each imputed dataset. The primary analysis, as described in Section 8.2.2, will be repeated for the Efficacy Population using the MI with MNAR assumption datasets.

Sensitivity 2: Tipping point

Additionally, a tipping point sensitivity analysis will be conducted for each dose compared to placebo at Week 24 if the result of the MI analysis is statistically significant at the alpha ≤ 0.025 level, in favor of treatment, for the given dose. The tipping point analysis will use the primary MAR assumption datasets, where all imputed values are adjusted.

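### Should the 95% confidence intervals in SAP 8.2.2 be 97.5% intervals, because each dose is tested at two-sided 0.025?

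*SAP*

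**What the plan says.** SAP 8.1.4 sets the testing level for the primary and key secondary endpoints: a two-sided 0.025 "alpha-level will be allocated to each dose for comparison with placebo to adjust for multiplicity of testing associated with two doses". Once p exceeds 0.025 for a dose, "inference for additional endpoints is no longer alpha-level protected for that dose group; however, nominal p-values will still be reported".

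SAP 8.2.2 pools the Mantel-Haenszel risk difference over 100 imputed datasets and reports the p-value together with "the combined treatment differences, combined standard errors, and 95% confidence intervals (CI".

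The key secondary endpoints borrow that method. For SALT ≤20 at Weeks 20, 16, 12 and 8, SAP 8.3.2 says "These endpoints will be assessed according to Section" 8.2.2. SAP 8.3.1 (SPRO at Week 24) borrows 8.2.2 by similarity, but its reporting sentence names no interval: "The observed number and percentage of SPRO responders by treatment group will be reported along with the appropriate p-values".

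Two conventions in SAP Section 4 bear on how results are read: "P-values which are significant at a 0.05, 0.025, 0.01, 0.001, or 0.0001 level will be marked with asterisks" and "P-values are descriptive for outcomes and analyses not included in the multiplicity algorithm". The tipping-point analysis in SAP 8.2.3 is run only if the result is "statistically significant at the alpha ≤ 0.025 level, in favor of treatment, for the given dose".

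**The concern.** A two-sided test at 0.025 and a 95% interval need not agree. If p falls between 0.025 and 0.05, the plan calls the comparison not significant while the reported interval excludes zero. The body of the SAP neither names a 97.5% interval nor labels the 95% one as unadjusted. Its cautions in Section 4 and in 8.1.4 concern p-values only. Section 4 also marks p-values significant at 0.05, with no exception for comparisons inside the hierarchy, and 8.2.2 allows a graphical display that might not carry the p-value.

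The risk is that a reader takes a failed dose comparison as a success. If the 95% intervals were ever used as the decision rule for both doses, the Bonferroni bound on the familywise error would be 0.05 + 0.05 = 0.10 instead of 0.05.

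**Working it through.** **Inputs.** Protocol 12.1 gives two-sided alpha 0.025, group sizes of 210 (12 mg), 350 (8 mg) and 140 (placebo), and response rates of 40%, 25% and 10%. The normal quantiles are 2.2414 for 97.5% intervals and 1.9600 for 95% intervals.

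**The plan's own power figure.** For 8 mg the pooled rate is (87.5 + 14)/490 = 0.2071. Since 1/350 + 1/140 = 0.0100, the null SE is √(0.2071 × 0.7929 × 0.0100) = 0.0405. The unpooled SE is √(0.25×0.75/350 + 0.10×0.90/140) = 0.0343.
- Power is Φ[(0.15 − 2.2414×0.0405)/0.0343] = 95.8%.
- With a continuity correction of 0.005 it is 94.3%, which matches the stated figure of about 94%.
- For 12 mg, power exceeds 99.99% (stated: above 99%).

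The plan was therefore powered at 0.025, and the interval level does not enter that calculation.

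**Width.** The ratio of half-widths is 2.2414/1.9600 = 1.144. At the planned rates:

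| Comparison | SE | 95% half-width | 97.5% half-width |
|---|---|---|---|
| 8 mg vs placebo | 0.0343 | 6.7 points | 7.7 points |
| 12 mg vs placebo | 0.0423 | 8.3 points | 9.5 points |

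**Where the two can disagree.** Take 59/350 on 8 mg against 14/140 on placebo, a difference of 6.9 points.
- Unstratified, complete data: SE 0.0323, z = 2.123, p = 0.034. The 95% interval is +0.5 to +13.2 and the 97.5% interval is −0.4 to +14.1.
- Planned stratified Mantel-Haenszel estimate with Sato variance, under three assumed stratum splits (partial; complete or near-complete):
  - 45/175 vs 11/70; 14/175 vs 3/70: p = 0.0295.
  - 50/210 vs 12/84; 9/140 vs 2/56: p = 0.0300.
  - 40/140 vs 9/56; 19/210 vs 5/84: p = 0.0298.
- In all three splits the 95% lower limit is +0.66 to +0.68 and the 97.5% lower limit is −0.20 to −0.23.

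With placebo fixed at 14/140, the unstratified conflict zone is 58 to 60 responders of 350 (8 mg) or 36 to 38 of 210 (12 mg). The stratified zone for 8 mg, moving responders within those splits, is 57 to 59. At 57, p is 0.0445 to 0.0458; at 60, p is 0.0236 to 0.0243 and the test passes. The zone shifts with the split.

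**How likely that is.** The standardized effects at the planned rates are 0.15/0.0343 = 4.37 (8 mg) and 0.30/0.0423 = 7.10 (12 mg). The chance of landing between the two critical values is Φ(2.2414 − θ) − Φ(1.9600 − θ).
- 8 mg: 0.87%. Exact binomial enumeration with the unpooled Wald statistic gives 1.3%.
- 12 mg: 0.00005%; exact 0.0002%.
- With placebo at 10% and assumed 8 mg rates of 22%, 20% and 17%, the exact values are 3.9%, 6.5% and 9.5%. Those rates are not in the documents, which give none for the key secondary endpoints.

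**Which rules use an interval.** None does. The hierarchy in 8.1.4 stops on p > 0.025, 8.3.1 tests both doses at 0.025, and 8.2.3 starts the tipping-point analysis on significance at 0.025. The allocated alpha sums to 0.025 + 0.025 = 0.05, as intended.

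**The case for a change.** The best argument for a change is that it is cheap and that nothing in the SAP's body tells a reader how to take the interval. The key secondary endpoints include SALT ≤20 as early as Week 8. Effects there may be smaller, and the conflict is more likely when effects are small. A 97.5% interval would match the test at the cost of one software setting.

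Some of this stands. The label is absent from the body text, and a conflict on a key secondary endpoint cannot be ruled out. Three things limit it.

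- The p-value is reported beside the interval to four decimals, and 0.025 is one of the levels that Section 4 marks in its own right. Whether the marks differ by level depends on table shells that are attachments and not available here. Those shells may already carry a footnote, and Section 4 allows minor changes to them without re-approving the SAP.
- Changing the level would not settle the reading. Suppose SPRO fails for a dose at p = 0.03 and Week 20 SALT then gives p = 0.01. The Week 20 97.5% interval excludes zero, yet that endpoint is not alpha-protected. Only the order of testing and the p-values show this.
- The SALT and SPRO responder endpoints in 8.4 also borrow 8.2.2 and are tested at 0.05, so 95% is the matching level there. A blanket switch in 8.2.2 would create the opposite mismatch.

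**Conclusion.** No change to the plan is needed. The interval level and the test level do differ, but a 95% interval reported beside a Bonferroni-split test is a common and valid estimate of precision, and every confirmatory rule is stated in terms of p against 0.025. Following the SAP as written gives the right decisions, with type I error and power unaffected.

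What remains is a missing label that a competent analyst supplies in a table footnote. On the primary endpoint it would matter visibly in about 1% of trials for 8 mg and almost never for 12 mg. This rests on the planned rates and group sizes, on complete data and on an unstratified calculation. If the true effect were much smaller the chance could approach 10% (9.5% at an assumed 17% against 10%), and the consequence would still be confined to presentation.
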